Three physician assessors who will be trained in the evaluation of skin punch biopsy wounds and the scoring criteria that will be used in this study will assess the wound and record their evaluations individually.

SAMPLE SIZE AND STATISTICAL ANALYSIS

Using G*Power 3.1.9.7, a minimum of 56 patients or 28 per group are required for this study based on the 8.38 mean Scar appearance score on Hydrocolloid

dressing versus 7.23 mean Scar appearance score on Conventional daily dressing.^[15] This computation also accounts for desired 1.5 common standard deviation, 5% level of significance and 80% power.

Descriptive statistics will be used to summarize the demographic and clinical characteristics of the patients. Frequency and proportion will be used for categorical variables and mean and SD for normally distributed continuous variables. Independent Sample T-test and Fisher's Exact/Chi-square test will be used to determine the difference of mean and frequency, respectively, between patients undergoing Hydrocolloid Dressing versus Topical Antibiotic. All statistical tests will be two tailed tests. Shapiro-Wilk test will be used to test the normality of the continuous variables. Missing values will neither be replaced nor estimated. Null hypotheses will be rejected at 0.05 α -level of significance. STATA 13.1 will be used for data analysis.

Inter-rater and Intra-rater reliability will also be conducted.

SAFETY EVALUATION

Assessment of possible adverse effects due to the hydrocolloid dressing or the topical antibiotics will be done on follow-up visit. Complaints of pruritus, burning, or stinging sensation will be asked from participants, while other physical signs and symptoms of adverse effects to the treatment applied will be checked by the primary investigator.

ETHICAL CONSIDERATIONS

This study will be conducted in accordance with the accepted ethical research practices of the ICH Good Clinical Practice regulations and guidelines. The study will

be explained thoroughly to the eligible patients prior to enrollment. Free and informed written consent will be obtained.

INFORMED CONSENT

All participants involved in the study will not be compromised in terms of treatment. All possible benefits and side effects of the treatment will be fully explained and must be understood by the patients prior to enrollment into the study.

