The possible side effect of hydrocolloid dressing is irritation of the skin. Treatment on patients who will experience any adverse side effects will be immediately stopped.

To minimize the risk of COVID-19 exposure, all safety measures in accordance with the IATF guidelines will be observed.

BENEFITS

The benefit that the patient will acquire from this study is better clinical outcomes of the post-biopsy site. This study can also help reduce medical costs and patients are suggested with alternative options which can be potentially used as one of the treatment modalities for post-biopsy sites.

INCENTIVES AND COMPENSATION

All of the dermatologic consultations and medications of the participants for the duration of the study will be free of charge. Transportation allowance of PHP 100.00 will be provided to the participant on their visit on the 5th day. Management, consultation, and treatment of adverse effects resulting from the participation in this study will be free of charge. No other form of monetary compensation will be provided to the patients for their participation. Patients will be informed of the results of the study once it has been completed.

SCORING CRITERIA FOR EVALUATION OF WOUND

Objective assessment is based on a study by Armstrong et. al. in 1986 entitled "Punch biopsy wounds treated with Monsel's solution or a collagen matrix".^[16] For this study, the assessment will be done as follows:

(1) infection (absent, millimeters of surrounding erythema or equivocal findings; or present, as inferred by indurated erythema or purulent discharge);

- (2) clinical estimate of reepithelialization (rated on a scale of (a) 0% to 25%, (b) 26% to 50%, (c) 51% to 75%, and (d) 76% to 100%);
- (3) clinical estimate of wound closure (rated on a scale of (a) 0% to 25%, (b) 26% to 50%, (c) 51% to 75%, and (d) 76% to 100%)
- (4) scar formation (unhealed; depressed or atrophied; normal fine-line scar; or hypertrophied scar or keloid);
- (5) pigmentation of scar (indeterminate or unhealed; normal; hyperpigmented; or hypopigmented);
- (6) cosmetic appearance of wound (acceptance of patient: indeterminate or unhealed; poor; fair; good; excellent)

DUMMY TABLES

Table 1. Baseline demographic and clinical characteristics

	Total	Hydrocolloid	Topical	P-value
		Dressing	Antibiotic	
Frequency (%); Mean \pm SD				
Age, years				
Sex				
Male				
Female				
Indications for Skin				
Punch Biopsy				
...				

Table 2. Scoring Criteria for Evaluation of Wound

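### Efficacy results are planned as frequencies by arm and a p-value, with no between-arm difference or confidence interval, although 28 patients per arm leave wide uncertainty

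*Combined protocol and SAP*

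**What the plan says.** The section Sample Size and Statistical Analysis is the whole analysis plan. It summarises categorical variables by frequency and proportion and continuous ones by mean and SD. For the comparison of arms it says "Independent Sample T-test and Fisher's Exact/Chi-square test will be used to determine the difference of mean and frequency, respectively". It adds "All statistical tests will be two tailed tests" and "Null hypotheses will be rejected at 0.05". The sample size is "a minimum of 56 patients or 28 per group are required for this study".

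The Dummy Tables section gives one efficacy shell, "Table 2. Scoring Criteria for Evaluation of Wound". Its columns are the total, the two arms and a p-value, and its cells hold frequencies with percentages. Its rows are the six wound items: infection (two levels); re-epithelialization, wound closure, scar formation and scar pigmentation (four levels each); and cosmetic appearance (five levels).

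The Project Summary, under Expected Outcomes, names a primary outcome: a proportion of patients with better overall healing. That outcome has no row in Table 2 and no stated effect measure. No section mentions a risk difference, risk ratio, odds ratio, reported mean difference or confidence interval.

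**The concern.** The main objective is to determine efficacy against mupirocin gauze, and the Significance of the Study section hopes the result will lead dermatologists to use less routine topical antibiotic. Both uses need two things from the trial: an estimate of how far healing differs between the arms, and the range of differences that the data leave open.

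The planned output gives the raw percentages and a test. The wording about determining the difference describes significance testing. A t-test could carry an interval for a mean difference, but all six wound items are categorical, so efficacy rests on Fisher's exact or chi-square tests, which do not produce one. With a small trial and a 0.05 threshold, the risk is that a non-significant result is read as evidence that the dressings perform alike, when the data would still allow an important difference in either direction.

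**Working it through.** **1. The plan's own sample size.** Inputs from Sample Size and Statistical Analysis: "8.38 mean Scar appearance score on Hydrocolloid", "7.23 mean Scar appearance score on Conventional daily dressing", and "desired 1.5 common standard deviation, 5% level of significance and 80% power", two-sided.

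- Standardised difference: (8.38 - 7.23)/1.5 = 1.15/1.5 = 0.767.
- Two-sample t-test (noncentral t): 27.70 per group, rounded up to 28. Power at 28 per group is 80.4%.

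The stated 28 per group reproduces. The sample size arithmetic is not at issue.

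**2. Precision at 28 per arm for a two-level outcome.** The documents give no event rates, so a range is assumed. The approximate 95% half-width for a difference between two arms with a common rate p is 1.96 × √[2p(1 - p)/28].

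| Assumed rate in both arms | Half-width, percentage points |
|---|---|
| 50% | ±26.2 |
| 70% | ±24.0 |
| 80% | ±21.0 |
| 90% | ±15.7 |

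**3. Newcombe intervals for assumed counts.** With Wilson limits (l, u) for each arm and D = p1 - p2:

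- lower limit = D - √[(p1 - l1)² + (u2 - p2)²]
- upper limit = D + √[(u1 - p1)² + (p2 - l2)²]

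For 20/28 v 14/28: p1 = 0.714 with Wilson limits 0.529 to 0.847; p2 = 0.500 with limits 0.326 to 0.674.

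- D = 0.214
- lower = 0.214 - √(0.185² + 0.174²) = 0.214 - 0.254 ≈ -0.04
- upper = 0.214 + √(0.133² + 0.174²) = 0.214 + 0.219 = 0.433

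| Assumed counts, hydrocolloid v mupirocin | Difference, points | Newcombe 95% CI | Fisher p, two-level split |
|---|---|---|---|
| 14/28 v 14/28 | 0 | -25 to +25 | 1.0 |
| 17/28 v 14/28 | +11 | -15 to +34 | 0.59 |
| 20/28 v 14/28 | +21 | -4 to +43 | 0.17 |
| 21/28 v 14/28 | +25 | -0.3 to +46 | 0.097 |
| 1/28 v 2/28 (rare event, such as infection) | -3.6 | -19.3 to +11.5 | 1.0 |

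**4. What these p-values are not.** A two-level test would apply to infection, and to the primary outcome if it is defined as yes or no. The other five rows of Table 2 keep four or five levels, so their p-values depend on the whole distribution. Keep the top re-epithelialization band at 20/28 v 14/28 and vary the lower bands (assumed counts, lowest to highest):

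- 0, 2, 6, 20 v 6, 4, 4, 14: chi-square 8.13 on 3 df, p = 0.043
- 2, 2, 4, 20 v 4, 4, 6, 14: chi-square 2.79 on 3 df, p = 0.42

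The difference in the top band, and its interval, are the same in both cases, yet the planned test falls on opposite sides of 0.05.

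**The case against.** The strongest reply is that Table 2 already shows the percentage at every level for each arm. The 20/28 v 14/28 case would read 71% v 50%, so size and direction are visible and anyone can subtract. An interval can also be computed from the published counts. This stands in part. A reader might infer that the trial would never say how much better healing is, and the documents do not support that: what is missing is a stated difference and its precision.

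Three other inferences go too far.

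- **That the examples above would simply appear in Table 2 as non-significant.** Most rows are tested on four or five levels, and step 4 shows that the first example could come out on either side of 0.05.
- **That the investigators will ignore the percentages when drawing conclusions.** The 0.05 rule is a testing threshold. No section says how the percentages will be weighed; the plan just gives the interval no role.
- **That any non-significant result is compatible with both large benefit and appreciable harm.** This depends on the data. At 20/28 v 14/28 the interval reaches only 4 points below zero.

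It is also fair to say that the choice of effect measure is not automatic. The documents set no success cut-point on the graded scales, and collapsing an ordered scale loses information. That is a reason to settle the measure in advance, since a cut-point chosen after the results are known could favour one arm.

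**Conclusion.** The point holds as a gap in estimation. The analysis text and the sponsor's own table shell agree on frequencies by arm plus a p-value, so this is the stated output and not a detail left unmentioned. At 28 per arm the unreported uncertainty is about ±16 to ±26 points for a two-level outcome with rates from 90% down to 50%. Even identical observed rates of 50% would leave a 25-point disadvantage or advantage open, so a non-significant result could not be taken as similarity.

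These figures assume the event rates and counts shown, a full 28 assessed patients per arm, and a two-level outcome. With fewer assessed patients the intervals would generally be wider. The trial remains analysable without the change, so this is a correction that should be made and not a fatal flaw.

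**What to change.** 1. Add a column to Table 2: *Difference, hydrocolloid minus mupirocin (95% CI)*, with the number of patients assessed in each arm.
2. Add a row for the stated primary outcome. This requires a patient-level definition of better overall healing, and a rule for combining the three assessors' individual ratings, which the plan does not give.
3. Fix the effect measure for each item before data are seen:
   - primary outcome and infection: risk difference with a Newcombe interval;
   - re-epithelialization, wound closure and cosmetic appearance: one measure each with a 95% CI, either the difference in the proportion in a prespecified top category (for example 76% to 100%, or good/excellent; both are proposals of this review and not cut-points in the protocol) or an ordinal measure such as a common odds ratio;
   - scar formation and pigmentation: difference in the proportion rated normal, with a 95% CI.
4. Add to Sample Size and Statistical Analysis that efficacy conclusions will rest on the estimate and its interval together with the p-value, and that a non-significant p-value will not be read as similarity.

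The cost is a short addition to the text, one column, one row and a choice of measure per item. No new data, visits or patients are needed. The main effort is agreeing the measures, which also depends on the primary outcome being defined.

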**A Double-Blind Randomized Controlled Trial on the Efficacy of Hydrocolloid
Dressing vs. Topical Antibiotic on Wound Healing of Post-Punch Biopsy
Wounds Among Patients in a Tertiary Hospital in Manila**

[name] [name]

[name], FPDS

University of Santo Tomas Hospital, [name]

Department of Dermatology

TITLE: A Double-Blind Randomized Controlled Trial on the Efficacy of Hydrocolloid Dressing vs. Topical Antibiotic on Wound Healing of Post-Punch Biopsy Wounds Among Patients in a Tertiary Hospital in Manila

[name], [name]

Resident, Department of Dermatology; Consultant, Department of Dermatology

PROJECT SUMMARY

Rationale:

Objectives: The main objective of this study is to determine the efficacy of using hydrocolloid dressing on wound healing of post-punch biopsy wounds vs topical antibiotic. Specifically, it aims to measure the following parameters: the presence or absence of infection, the clinical estimate of reepithelialization, the clinical estimate of wound closure, scar formation, pigmentation of scar, and the cosmetic appearance of the wound.

Methodology and Population: The study is a double-blind randomized controlled trial which will be conducted at the Dermatology outpatient department and the private clinics of dermatology consultants of the University of Santo Tomas Hospital. Patients who will be included are those who are 18 to 64 years of age with clean cutaneous lesions. Excluded from this study are those who have infected wounds, those who have conditions with poor tendency to heal including diabetes mellitus, peripheral vascular disease, history of keloid formation, those currently receiving anticoagulation therapy or systemic corticosteroids, and those known to have hypersensitivity to topical antibiotics.

Time Frame: 6 months

Expected Outcomes: The primary outcome measure is the proportion of patients who achieved better overall healing when treated with hydrocolloid dressing.

GENERAL INFORMATION**PROTOCOL TITLE:**

**A DOUBLE-BLIND RANDOMIZED CONTROLLED TRIAL ON THE
EFFICACY OF HYDROCOLLOID DRESSING VS. TOPICAL ANTIBIOTIC ON
WOUND HEALING OF POST-PUNCH BIOPSY WOUNDS AMONG
PATIENTS IN A TERTIARY HOSPITAL IN MANILA**

NAME AND ADDRESS OF SPONSOR/FUNDER:

NOT APPLICABLE

NAME AND ADDRESS OF AUTHORS:

[name] [name]

[name], FPDS

University of Santo Tomas Hospital, [name]

BACKGROUND

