	Total	Hydrocolloid	Topical	P-value
		Dressing	Antibiotic	
Frequency (%)				
Infection				
Absent				
Present				
Re-epithelialization estimate				
0 to 25%				
26 to 50%				
51 to 75%				
76 to 100%				
Wound closure				
0 to 25%				
26 to 50%				
51 to 75%				
76 to 100%				
Scar Formation				
Unhealed				

Depressed or Atrophied

Normal Fine-Line Scar

Hypertrophied Scar or
Keloid

Scar Pigmentation

Indeterminate or Unhealed

Normal

Hyperpigmented

Hypopigmented

Cosmetic Appearance

Indeterminate or Unhealed

Poor

Fair

Good

Excellent

REFERENCES

2. Mendonça RJ de, Coutinho-Netto J. Cellular aspects of wound healing. *Anais Brasileiros de Dermatologia*. 2009;84(3):257-262.
doi:<https://doi.org/10.1590/s0365-05962009000300007>
3. Lazarus GS. Definitions and Guidelines for Assessment of Wounds and Evaluation of Healing. *Archives of Dermatology*. 1994;130(4):489.
doi:<https://doi.org/10.1001/archderm.1994.01690040093015>
doi:<https://doi.org/10.1097/01.asw.0000416006.55218.d0>
5. Thomas S. Hydrocolloid dressings in the management of acute wounds: a review of the literature. *International Wound Journal*. 2008;5(5):602-613.
doi:<https://doi.org/10.1111/j.1742-481x.2008.00541.x>
6. Viciano, José E. Castera, J V. Effect of Hydrocolloid Dressings on Healing by Second Intention after Excision of Pilonidal Sinus. *The European Journal of Surgery*. 2000;166(3):229-232.
doi:<https://doi.org/10.1080/110241500750009339>

doi:<https://doi.org/10.1097/00000637-199401000-00011>
9. Hultén L. Dressings for surgical wounds. *The American Journal of Surgery*. 1994;167(1A):S42-S45. doi:[https://doi.org/10.1016/0002-9610\(94\)90010-8](https://doi.org/10.1016/0002-9610(94)90010-8)

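### Three ordered healing items go to Fisher/chi-square, which ignores grade order and loses power, and no rule turns three assessors' grades into one value per patient

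*Combined protocol and SAP*

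**What the plan says.** Sample Size and Statistical Analysis names two between-group methods: an independent t-test for means and, for frequencies, Fisher's "Exact/Chi-square test will be used to determine the difference of mean and frequency, respectively, between patients undergoing Hydrocolloid Dressing versus Topical Antibiotic". No rank, trend or ordinal-model test appears anywhere.

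The outcomes are defined under Scoring Criteria for Evaluation of Wound:

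- Re-epithelialization has four ascending bands ("clinical estimate of reepithelialization (rated on a scale of (a) 0% to 25%, (b) 26% to 50", and so on up to 76–100%). Wound closure uses the same bands.
- The sixth item is "cosmetic appearance of wound (acceptance of patient: indeterminate or unhealed; poor; fair; good; excellent".
- Infection is binary. Scar formation and pigmentation are types rather than grades.

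Dummy Table 2 reports all six items, from infection and "Re-epithelialization estimate" onwards, as frequencies and percentages with a P-value column and no means.

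Under F. Assessment, three trained physician assessors "will assess the wound and record their evaluations individually". The only further statement on multiple ratings is "Inter-rater and Intra-rater reliability will also be conducted". D. Baseline Data Collection has the physician assessors record all six items on day 5, including cosmetic appearance.

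The Project Summary gives a different kind of primary outcome: "The primary outcome measure is the proportion of patients who achieved better overall healing when treated with hydrocolloid dressing".

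**The concern.** Re-epithelialization and wound closure are ordered, and so is cosmetic appearance from poor to excellent. Chi-square and Fisher's exact test give the same p-value however the grades are relabelled, so they spread their sensitivity over every possible pattern of difference. The trial's hypothesis is one particular pattern: a shift towards better healing. With 56 patients, such a shift is more likely to be missed on the items that describe healing. The plan also names no single effect measure with a confidence interval for these items.

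The second gap concerns the unit of analysis. The comparison is between patients, but each patient may have three different grades on an item. Reliability statistics measure agreement; they do not produce one value per patient. Without a rule, someone must choose the value later, possibly with results in view.

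Cosmetic appearance has two further open points. Its indeterminate or unhealed category has no clear rank, and its label points to the patient while another section has the assessors record it.

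**Working it through.** **1. Reproduce the plan's sample size.** Inputs from Sample Size and Statistical Analysis: means 8.38 and 7.23, SD 1.5, "5% level of significance and 80% power", two-tailed tests. The effect is (8.38 − 7.23)/1.5 = 1.15/1.5 = 0.767 SD. A two-sided two-sample t-test (noncentral t) has 78.9% power with 27 per arm and 80.4% with 28, so 28 per arm, 56 in total, is confirmed. That figure is for a t-test on a continuous scar score, which is not one of the six listed items.

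**2. A worked example of what ignoring order costs.** Illustrative counts from lowest to highest grade: control 8/9/7/4, hydrocolloid 3/6/8/11.

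- *Chi-square.* Column totals are 11, 15, 15, 15, so expected counts per arm are 5.5, 7.5, 7.5, 7.5. X² = 2 × (2.5²/5.5 + 1.5²/7.5 + 0.5²/7.5 + 3.5²/7.5) = 6.21 on 3 df, p = 0.10. Fisher's exact gives p = 0.11. Shuffling the grade labels leaves chi-square at 0.10.
- *Wilcoxon.* Midranks are 6, 19, 34, 49. The control rank sum is 8×6 + 9×19 + 7×34 + 4×49 = 653, against an expected 28 × 57/2 = 798. The tie-corrected variance is (28²/12) × [57 − 11,400/(56 × 55)] = 3,482, so z = −145/59.0 = −2.46 and p = 0.014.

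**3. Power at 28 per arm.** The documents give no grade distribution, so 11 control distributions were assumed. The 0.767 SD effect was applied as a uniform shift on an underlying normal scale (two-sided 0.05, 40,000 runs per setting).

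| Control grades, % (low to high) | Chi-square | Wilcoxon |
|---|---|---|
| 25/25/25/25 | 0.55 | 0.73 |
| 10/20/30/40 | 0.48 | 0.68 |
| 5/15/30/50 | 0.42 | 0.63 |
| 40/30/20/10 | 0.57 | 0.75 |
| 50/30/15/5 | 0.56 | 0.74 |
| 10/40/40/10 | 0.54 | 0.73 |
| 2/5/23/70 | 0.30 | 0.50 |
| 2/5/13/80 | 0.18 | 0.39 |
| five equal grades | 0.51 | 0.75 |
| 10/15/25/30/20 | 0.49 | 0.74 |
| 30/25/20/15/10 | 0.53 | 0.76 |

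- The loss is about 17–25 points. It is 12–19 points at 0.5 SD and 10–28 at 1.0 SD.
- Fisher's exact, run on 25/25/25/25, 10/20/30/40, 5/15/30/50 and 2/5/23/70, has power 0.56, 0.51, 0.46 and 0.36 against Wilcoxon 0.73, 0.68, 0.63 and 0.51: a loss of about 15–17 points.
- Proportional-odds shifts (odds ratios 2 to 5, six control distributions) give a similar loss of about 10–25 points.
- With no true difference, rejection rates are 0.028–0.048 for chi-square and 0.047–0.050 for Wilcoxon. Both are valid.
- In six of the distributions, chi-square needs about 40–45 per arm to match Wilcoxon at 28.

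**4. The combining rule.** Set side by side, the plan has three separate grades per wound, a between-patient comparison, and a reliability analysis. No mean, median, majority, consensus or adjudication step links them. As a purely hypothetical bound, suppose all three ratings were entered in a chi-square test as if independent. With four equal grades, type I error would be about 10%, 15% and 23% at assumed inter-rater correlations of 0.4, 0.6 and 0.8. The median grade with a Wilcoxon test stays at 0.047–0.051.

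**The case against.** The planned test is valid, the plan does not contradict itself here, and the primary outcome is a proportion for which Fisher/chi-square is suitable. This is correct: the first part is about efficiency, not error, and it covers three items out of six.

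The sizes rest on assumptions. The effect comes from a different score, and a uniform shift favours a rank test. That stands too. For differences that are not a shift the ranking can reverse: in an invented case (10/40/40/10 against 30/15/15/40), chi-square has about 93% power and Wilcoxon 11%. A shift is nevertheless what the hypothesis of better healing implies, and the loss was at least about 10 points in every shift examined.

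Many assumed settings have small expected counts, where Fisher's exact would usually replace chi-square. The four Fisher settings above still show a clear loss; further, smaller runs showed about 18–24 points.

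Only re-epithelialization and wound closure are ordered beyond doubt. If cosmetic appearance is the patient's own rating, no assessor rule is needed for it. Arm-level percentages will also be shown, so differences can be read from the table; what is missing is a summary effect with its interval.

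Finally, nobody has proposed entering all ratings as independent, so the inflated error rates illustrate a risk and carry no weight in judging severity.

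**Conclusion.** Both parts hold. That the plan names no order-respecting test and no combining rule is plain from the text. The cost of the first gap is about 17–25 points of power at 28 per arm (four equal grades: 55% against 73%), conditional on a uniform shift of 0.767 SD and on assumed control distributions. The cost of the second cannot be put as a single number: the analysed value is undefined and open to choice after the fact.

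The change should be made, but the trial is not invalid without it. Nor does it restore full power: Wilcoxon power stays below 80% in all 11 settings at this effect. With four equal grades, 80% would need about 34 per arm by Wilcoxon and about 46–48 by chi-square.

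**What to change.** Add to Sample Size and Statistical Analysis, before any outcome data are seen:

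- **Test.** Re-epithelialization, wound closure and cosmetic appearance will be compared by two-sided Wilcoxon rank-sum test at 0.05, reporting the probability of superiority (or an unadjusted common odds ratio) with 95% CI. Infection, scar formation, pigmentation and any binary primary outcome keep Fisher's exact/chi-square.
- **One value per patient per item.** Use the median of the three assessors' grades for ordered items and the majority for infection, scar formation and pigmentation. State a rule for when all three differ and for when only two grades are available. Individual ratings are used only for reliability.
- **Cosmetic appearance.** State who rates it; if the patient does, use that single rating. Fix the handling of indeterminate or unhealed. For example, rank unhealed lowest, report indeterminate separately by arm, and repeat the test with indeterminate ranked lowest.

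The cost is a few sentences, standard commands in the package already named, and at most one response label split in two. No new patients or visits are needed. Because a rank test is less sensitive to differences that are not a shift, keep the full frequencies in Table 2.

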Specifically, this study aims to compare the efficacy of hydrocolloid dressing after 5 days post-punch biopsy by measuring the following parameters: absence or presence of infection, clinical estimate of reepithelialization, clinical estimate of wound closure, scar formation, pigmentation of scar and cosmetic appearance of wound.

METHODOLOGY

A. Study Design

This is a double blind randomized controlled trial that will be conducted at the outpatient department of the University of Santo Tomas Hospital Department of Dermatology. Permission letters from the Head of Ambulatory Care Services (ACS), the Data Privacy Officer (DPO), and the Medical Director of UST Hospital will be obtained prior to the implementation of this study. Permission letters from the USTH Dermatology consultants for their private patients will be obtained prior to the implementation of this study.

[figure not shown]

Figure 1. Schematic diagram of the study design

B. Patient Selection, Recruitment and Withdrawal

Adult patients 18 to 64 years old with clean cutaneous lesions who will undergo skin punch biopsy using a 3-mm disposable biopsy puncher shall be included in the study.

Patients will be recruited from the UST Hospital outpatient department and from the private clinics of the UST Hospital Dermatology consultants. Patients who have infected wounds, patients who have conditions with poor tendency to heal including diabetes mellitus, peripheral vascular disease, history of keloid formation, patients currently receiving anticoagulation therapy or systemic corticosteroids, and patients known to have hypersensitivity to topical antibiotics shall be excluded from the study.

Participants may request to withdraw from the study at any time. A participant may also be withdrawn from the study if the primary investigator believes that the participant was non-compliant with the treatment guidelines or develops severe and intolerable adverse effects (e.g. hypersensitivity reaction) secondary to the treatment given.

C. Randomization and Blinding

Randomization

Assignment of participants to the experimental (hydrocolloid dressing) or control group (topical antibiotic) will be done using the fishbowl method by a research assistant.

Blinding

Participants and the physician assessors will be blinded with the treatment assigned.

D. Baseline Data Collection

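### The named primary outcome is undefined and has no row in the results table, which leaves six unranked wound items each tested at 0.05 with no multiplicity rule

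*Combined protocol and SAP*

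**What the plan says.** The Project Summary, under Expected Outcomes, states: "The primary outcome measure is the proportion of patients who achieved better overall healing when treated with hydrocolloid dressing". Nothing later says which ratings, or what combination of them, make a patient better overall.

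Specific Objectives lists what will be compared at day 5: "absence or presence of infection, clinical estimate of reepithelialization, clinical estimate of wound closure, scar formation, pigmentation of scar and cosmetic appearance of wound". The same six appear in the Project Summary objectives, in Baseline Data Collection and in the Scoring Criteria, never ranked. Specific Objectives places all six, infection included, under efficacy.

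The only outcome table among the Dummy Tables is "Table 2. Scoring Criteria for Evaluation of Wound". Its rows are these six items and it has a p-value column. It has no row for overall healing.

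Sample Size and Statistical Analysis assigns a t-test to means and Fisher's exact or chi-square to frequencies. It adds "All statistical tests will be two tailed tests" and "Null hypotheses will be rejected at 0.05". It mentions no multiplicity adjustment, hierarchy or success rule. The sample size rests on another variable again: "8.38 mean Scar appearance score on Hydrocolloid" dressing against "7.23 mean Scar appearance score on Conventional daily dressing", at "5% level of significance and 80% power".

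**The concern.** A single well-defined primary outcome would hold the false-positive rate of the efficacy conclusion at 5%, however many other items were tabulated. Here the named primary cannot do that, because it cannot be computed from the plan as written. The sample-size variable does not single out a primary either, since a mean scar appearance score is none of the six categorical ratings. What remains is six p-values, each judged at 0.05, with nothing to stop the analyst from choosing among them after seeing the data.

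The Significance section says that the results should encourage dermatologists to cut back routine prophylactic topical antibiotics. One chance finding, for example on scar pigmentation at day 5, could be offered in support of that. Such a choice cannot be repaired credibly once results by arm are known.

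**Working it through.** **1. The plan's own figure.** Difference 8.38 − 7.23 = 1.15; SD 1.5; standardised difference 1.15/1.5 = 0.767; two-sided alpha 0.05. The normal approximation gives 27 per group. The noncentral t gives power of 78.9% at 27 and 80.4% at 28. The stated 28 per group (56 in total) is reproduced, for a t-test on a mean score.

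**2. Six independent, exact 5% tests.** 1 − 0.95^6 = 26.5%. If infection is so rare that it contributes almost nothing, five tests give 1 − 0.95^5 = 22.6%.

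**3. Correlated tests.** The documents give no correlation between items, so it is assumed. For six equicorrelated normal test statistics (200,000 draws each), the chance of at least one rejection is 24.3% at correlation 0.3, 20.9% at 0.5, 16.4% at 0.7 and 11.0% at 0.9.

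**4. The planned tests at 28 against 28.** Six categorical items were cut from correlated latent normals (correlation 0, 0.5 and 0.8) with no difference between arms, and tested at 0.05 by the exact test and by chi-square. The documents give no category frequencies, so all of those below are assumptions. Scar, pigmentation and cosmetic frequencies start with the unhealed category.

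| Assumed frequencies | At least one p<0.05 |
|---|---|
| Infection 20%, all other items evenly spread | 20% to 29% |
| Infection 3%; re-epithelialization and closure 10/25/35/30%; scar 40/25/30/5%; pigmentation 40/30/25/5%; cosmetic 20/10/25/30/15% | 16% to 23% |
| Infection 2%; re-epithelialization and closure 10/30/40/20%; scar and pigmentation 90/5/4/1%; cosmetic 30/10/25/25/10% | 15% to 17% |
| Infection 3%; scar and pigmentation 92% unhealed; cosmetic 85% unhealed | 12% to 15% |
| Infection 3%; scar and pigmentation 95% unhealed; cosmetic 90% unhealed; re-epithelialization and closure 65% in the top band | 7% to 10% |

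The first three rows use 2,000 trials per setting and the last two use 800. The Monte Carlo standard error is about one percentage point: √(0.2×0.8/2000) = 0.9 points and √(0.08×0.92/800) = 1.0 point. Further runs under similar assumptions gave 19% to 22% for spread ratings, about 11% for mostly unhealed wounds and 6% to 9% for a more extreme case, so the ends of the range are approximate.

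The rate falls down the table because an item with nearly all patients in one category rarely reaches p<0.05. At 90% unhealed, the exact test on scar or pigmentation rejected in only 1.2% to 2.0% of trials. Infection at 2% or 3% essentially never did.

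**5. Direction.** All of these figures count differences either way. For directional tests, results favouring hydrocolloid alone give 1 − 0.975^6 = 14.1% if independent and 10.5% at correlation 0.5, against a nominal 2.5%.

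**6. With a rule in place.** One prespecified test gives 5%. Bonferroni at 0.05/6 = 0.0083 gives 1 − (1 − 0.0083)^6 = 4.9% if independent.

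**The case against.** The plan does name a single primary outcome, and it is a proportion. The general sentence on Fisher's exact or chi-square would cover it. A reader might infer that the primary has no test at all, but that goes too far: a test is available, and what is missing is the variable to apply it to. The multiplicity problem follows largely from that gap.

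Nor does the plan say that a single significant item will count as proof of efficacy. That the six stand on an equal footing is inferred from the unranked list and the silence on any success rule. The inference is fair, but it is not the plan's own statement.

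The strongest objection concerns size. A reader might infer that an ineffective dressing would look effective about one time in five, or at four times the nominal rate. The documents do not support this as a general figure. It holds when ratings are well spread, but three of the six items have an unhealed category, and at a single day-5 visit that category could hold most wounds. The rate then falls to near 10% or lower. A two-tailed count also includes results that favour the antibiotic, and a chi-square on four or five unordered categories may have no clear direction.

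All of this stands and limits the wording. It does not remove the defect, because the rate exceeded 5% in every scenario examined.

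**Conclusion.** The concern holds in this form: the primary outcome is named but undefined and untabulated, six unranked items carry the only specified efficacy p-values, and no rule governs their joint use. The 5% level does not apply to an efficacy conclusion drawn from whichever of the six is significant.

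The inflation is 26.5% under independence with exact tests, and roughly 7% to 29% for the planned tests at 28 per arm. Where in that range the trial would fall depends on category frequencies, correlation and choice of test, and the documents settle none of these. The direction of the error is certain and its size is not.

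Six may also be an undercount. Three assessors rate each wound individually and no rule combines their ratings, so further choices are open.

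**What to change.** Name one confirmatory outcome, in the same words, in the Project Summary, in Sample Size and Statistical Analysis, and in Table 2. There are two ways to do it:

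- Define better overall healing explicitly from the existing ratings and add its row to Table 2.
- Replace it with one item. Re-epithelialization is a candidate, since the Assessment section describes it as occurring in the days after injury.

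Changing only the analysis section would leave the Project Summary naming a different primary. The definition should also say how the three assessors' ratings become one value per patient.

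Then state that the efficacy conclusion rests on that test alone at two-sided 0.05. Either apply Holm's adjustment to the other items or report them without significance claims. Mark the primary row in Table 2.

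The text change is a few sentences and one table row or footnote. It has two costs. An isolated p<0.05 on another item can no longer support an efficacy claim. And a reader might infer that the change is free in power, which the documents do not support: the 80% refers to a mean scar appearance score, and the plan should say that it does not carry over to the chosen primary.

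As an illustration, suppose that the standardised difference of 0.767 applied on a latent scale to a four-level item. A chi-square at 28 per arm would then have about 55% power with even control categories, 47% with 10/20/30/40%, and 31% with 65% in the top band (assumed frequencies, 4,000 trials each). The chosen primary therefore needs its own sample-size justification. That need exists already and is not created by this change.
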